Short Title	PATRC
Protocol Number	18-1789
Phase	Pilot
Methodology	Four-session, crossover design, active sham controlled
Study Duration	This study is expected to last eighteen months.
Study Center(s)	This is a four-session and single-site study performed at The University of North Carolina at Chapel Hill.
Objectives (Purpose)	The purpose of this pilot study is to modulate oscillatory activity in the prefrontal cortex using rhythmic transcranial magnetic stimulation during performance of a cognitive control task.
Number of Participants	100 (until 48 are completed)
Diagnosis and Main Inclusion Criteria	Eligible participants will be healthy adults between the ages of 18-35 with no history of mental or psychiatric disorder.
Description of Intervention (Procedures/methods)	The participants will perform a cognitive control task. During the task, rhythmic trains of transcranial magnetic stimulation will be delivered. Electroencephalography will be collected throughout every session.
Related IRB Applications	17-0149

1.4 FUNDING SOURCES

Please list below the funding sources for this project:

Sponsor Name	UNC Ramses Number	Sponsor Type	Prime Sponsor Name	Prime Sponsor Type	Sponsor/Grant Number
N/A	N/A	N/A	N/A	N/A	N/A

External Funding: This project is not externally funded.

UNC-CH Funding: This project is not funded through UNC-CH.

Classified: This project is not classified.

2 INTRODUCTION

This document is a protocol for a human research study. This study is to be conducted according to U.S. and international standards of Good Clinical Practice (FDA Title 21 Part 312 and International Conference on Harmonization guidelines), applicable government regulations and Institutional research policies and procedures.

2.1 BACKGROUND

Neural oscillations are proposed to be a mechanism of coordinating information processing across distributed regions of cortex (Fries 2015). Different neural oscillations may correspond to different underlying neural computations (Wang 2010). Noninvasive brain stimulation allows experimenters to modulate specific neural oscillations by targeting particular frequency bands (Romei et al. 2016). By collecting simultaneous electroencephalography (EEG), rhythmic transcranial magnetic stimulation (TMS) has been previously demonstrated to entrain neural oscillations at the frequency of stimulation (Thut et al. 2011; Hanslmayr et al. 2014; Albouy et al. 2017). Furthermore, when the frequency of entrained neural oscillations is matched to the frequency of endogenous activity in a cognitive task, the brain stimulation improves behavioral performance (Albouy et al. 2017). Therefore, noninvasive brain stimulation is a promising tool for improving cognition by inducing optimal neural activity via externally applied electromagnetic fields; e.g. cognitive control improvements (Alekseichuk et al. 2016; Albouy et al. 2017; Reinhart 2017; Wolinski et al. 2018).

Previous evidence has implicated neural activity in the alpha band (8-12 Hz) in information suppression and activity in the theta band (4-7 Hz) in information processing (Klimesch et al. 2007; Dé et al., 2014). Cognitive control task paradigms have been shown to elicit distinct activity in both of these bands (Popov et al., 2018). In this task, the presented stimuli can be lateralized to the right and left visual field during encoding, while a cue informs participants which stimuli (right or left) are relevant to be remembered for testing later. In this paradigm, alpha activity in parietal cortex is found contralateral to irrelevant stimuli—supporting the role of alpha in information suppression—while theta activity in frontal cortex increases with the number of stimuli to be remembered—supporting the role of theta in active information processing (Wallis et al., 2015).

For the current study, we propose to deliver rhythmic trains of TMS in either alpha frequency, theta frequency, or an arrhythmic control to modulate neural processing during a cognitive control task. By collecting simultaneous EEG with TMS, we will be able to measure the entrained oscillations from rhythmic TMS. The goal of this experiment is to boost the observed theta and alpha activity that is seen with the successful prioritization and suppression of information during the task.

To provide causal evidence that parietal cortex generates alpha activity and frontal cortex generates theta activity, we will apply rhythmic TMS stimulation to two scalp location, the anterior middle frontal gyrus and inferior intraparietal sulcus. By applying alpha frequency, theta frequency, and arrhythmic TMS at each location, we will be able to examine the causal relationship of frontal theta oscillations to information prioritization and parietal alpha oscillations to information suppression.

2.2 DOSE RATIONALE

TMS is a safe, non-invasive, widely-used tool that applies focal electric fields to the brain using magnetic coils placed on the scalp (Rossi et al. 2009). On the first session of the study, participants will receive a motor thresholding procedure in which electrodes are attached to the first dorsal interosseous muscle of the right hand. The contralateral motor cortex will be targeted by single pulses of TMS until a motor evoked potential (MEP) is generated: defined as a near-instantaneous increase muscle activity greater than 200 microvolts. Next, the intensity of single pulse TMS will be lowered until an MEP is generated on five out of ten pulses. This is defined as the participant's motor threshold (Rossi et al. 2009). For the subsequent stimulation days, participants will receive TMS at 120% of their motor threshold. Participants will receive trains of 5 pulses at 5 hertz, 10 hertz, or arrhythmic randomized pulse intervals not to exceed an inter-pulse-interval of 20 milliseconds. Between every train will be at least 5 seconds. An inter-train-interval of 5 seconds or greater allows for any residual effects of stimulation to return to baseline. This intensity, inter-pulse-interval, and inter-train-interval is well within the safety guidelines set forth for repetitive TMS (Wassermann, 1998; Rossi et al., 2009) and has been used in similar paradigms as the one described here (Thut et al. 2011; Hanslmayr et al. 2014; Albouy et al. 2017). EEG will be collected using the Geodesic 400 system (EGI INC., Eugene, OR, USA). Collecting simultaneous EEG and TMS does not pose any additional risk over TMS on its own. EEG does not involve brain stimulation and is used purely for neuroimaging (minimal risk).

2.3 STUDY AIMS/HYPOTHESES

2.3.1 PRIMARY OUTCOME – WORKING MEMORY CAPACITY

RATIONALE. Participants make a button press on a keyboard to indicate if the probed items are matched or non-matched to the items held in memory. The investigators will calculate the accuracy for these responses and convert this to Pashler's working memory capacity metric for each condition. Theta oscillations are known to be generated in frontal cortex when cued to the contralateral visual field. Alpha oscillations are known to be generated in parietal cortex when cued to the ipsilateral visual field.

ALTERNATIVE HYPOTHESIS. When the frequency of TMS to either frontal or parietal cortex is compatible with the endogenous activity, working memory capacity should increase relative to TMS that is incompatible. Therefore, we will report the TMS compatibility effect as the average of "theta minus alpha TMS to frontal cortex for retro-cue right" and "alpha minus theta TMS to parietal cortex for retro-cue left". We will report the mean and standard deviation of the TMS compatibility effect across participants. This effect will be investigated using repeated-measures two-way ANOVA, and an interaction between TMS site and TMS frequency is hypothesized.

NULL HYPOTHESIS. There is no systematic effect of frequency specific TMS on working memory capacity.

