2.3.3 SECONDARY OUTCOME – RESPONSE TIME

RATIONALE. Participants make a button press on a keyboard to indicate if the probed items are matched or non-matched to the items held in memory. The investigators will calculate the response time for each condition. Theta oscillations are known to be generated in frontal cortex when cued to the contralateral visual field. Alpha oscillations are known to be generated in parietal cortex when cued to the ipsilateral visual field.

ALTERNATIVE HYPOTHESIS. When the frequency of TMS to either frontal or parietal cortex is compatible with the endogenous activity, response time should decrease relative to TMS that is incompatible. Therefore, we will report the TMS compatibility effect as the average of "theta minus alpha TMS to frontal cortex for retro-cue right" and "alpha minus theta TMS to parietal cortex for retro-cue left". We will report the mean and standard deviation of the TMS compatibility effect across participants. This effect will be investigated using repeated-measures two-way ANOVA, and an interaction between TMS site and TMS frequency is hypothesized.

NULL HYPOTHESIS. There is no systematic effect of frequency specific TMS on response time.

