6.5 COGNITIVE TASKS

6.5.1 COGNITIVE CONTROL TASK

The cognitive control task used in this paradigm consists of the presentation of colored squares on the left and right side of a computer screen. Stimuli are presented briefly, followed by a brief delay. After this, an arrow pointing to the left, right, or both left and right will briefly appear on the screen. This informs the participants which set of squares (left or right) they must remember and will be tested on. The cue is followed by another delay, and finally a new set of squares is presented. Participants press a button to indicate whether the squares are the same or different from the ones they originally saw. Between presentation of stimuli there is a small centrally presented fixation cross upon which participant maintain their gaze. Participants will complete 10 blocks of the task, each composed of 20-30 trials each. Participants will have a self-paced break between each of the blocks.

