10.1 SAFETY PARAMETERS

STIMULATION SIDE EFFECTS. A stimulation adverse effects questionnaire used in previous studies will be administered at the end of each stimulation. This questionnaire will be used as a safety measure and to collect data on participant experience. The adverse effects questionnaire asks participants to respond on a 4 point Likert scale on the severity of symptoms experienced during the stimulation session (1 = absent, 2 = mild, 3 = moderate, 4 = severe). The side effects listed are headache, neck pain, scalp pain, tingling, itching, ringing/buzzing noise, burning sensation, local redness, sleepiness, trouble concentrating, improved mood, worsening of mood, dizziness, flickering lights, and other (specify). Participants are also asked to rate on a 5 point Likert scale how related they believe the side effects to be to stimulation (1 = no relation, 2 = remote, 3 = possible, 4 = probable, 5 = definite).

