11.1 STATISTICAL ANALYSIS STRATEGIES

To control for non-specific effects of rhythmic TMS, we will use an active control: arrhythmic TMS (randomized inter-pulse-interval) that is matched to the target stimulation in number of pulses and temporal duration. All analyses will be run on the difference from condition-matched arrhythmic TMS. The key analysis is a two-way repeated-measures ANOVA with factors TMS frequency (theta vs alpha) and location (inferior-IPS vs anterior-MFG). Post-hoc t-tests will be run on a significant main effect of TMS frequency, TMS site, or interaction. We will use Tukey's adjusted significance for post-hoc testing to correct for multiple comparisons.

Primary outcome: working memory capacity. Two-way repeated-measures ANOVA run on the difference from arrhythmic TMS with factors (TMS site and TMS frequency). The direction of the retro-cue is held consistent for each site: for TMS to frontal cortex (anterior-MFG) the retro-cue to the right is used, and for TMS to parietal cortex (inferior-IPS) the retro-cue to the left is used. We hypothesize that theta frequency rhythmic TMS will improve behavioral performance when applied to anterior-MFG; i.e. a main effect of TMS frequency and/or an interaction between TMS frequency and cue. We hypothesize that alpha frequency rhythmic TMS will improve behavioral performance for retro-cue trials when applied to inferior-IPS; i.e. an interaction between TMS frequency and cue.

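### With cue direction fixed by site, the capacity and response-time compatibility effects cannot show cue specificity or exclude frequency-related distraction that differs between the two sites

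*Combined protocol and SAP*

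**What the plan says.** Sections 2.3.1 (working memory capacity) and 2.3.3 (response time) define the compatibility effect as a mean of two differences. The frontal half is "theta minus alpha TMS to frontal cortex for retro-cue right". The parietal half reverses the subtraction and uses the other cue direction: "alpha minus theta TMS to parietal cortex for retro-cue left". Capacity is expected to rise with compatible stimulation. For response time the expected sign is reversed: "response time should decrease relative to TMS that is incompatible".

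Section 11.1 analyses both outcomes with a two-way repeated-measures ANOVA whose factors are site and frequency, after subtracting arrhythmic TMS. It states: "The direction of the retro-cue is held consistent for each site". Right cues are used for the frontal site and left cues for the parietal site. The same section hypothesises an interaction between frequency and cue. For the frontal site it also accepts a main effect of frequency.

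On non-specific effects, section 11.1 says: "To control for non-specific effects of rhythmic TMS, we will use an active control: arrhythmic TMS". It describes this control as condition-matched, and as equal to the target trains in pulse count and duration. Section 6.2 lists three train types, one of them arrhythmic.

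In the task (section 6.5.1), "an arrow pointing to the left, right, or both left and right will briefly appear on the screen". Stimulation is given on every trial (section 5.2) and the frequencies are intermixed within every block (sections 4 and 4.1).

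**The concern.** The hypothesis in section 2.3.1 is cue-specific: frontal theta goes with the contralateral cue and parietal alpha with the ipsilateral cue. The contrast takes one cue direction at each site, so cue and site are aliased and cue specificity is never examined.

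The trains also differ physically. Five pulses span 4 × 200 = 800 ms at theta and 4 × 100 = 400 ms at alpha (section 6.2). Section 10.1 shows that sensory and attentional effects are anticipated: "The side effects listed are headache, neck pain, scalp pain, tingling, itching, ringing/buzzing noise, burning sensation, local redness, sleepiness, trouble concentrating". If one train type is more distracting than the other, and by a different amount at the two scalp sites, the compatibility effect moves away from zero with no oscillatory mechanism. For capacity it moves upward if alpha trains are relatively more disruptive frontally. With the opposite sign, a real effect could be hidden.

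At stake is the causal reading in section 2.1, frontal theta for prioritisation and parietal alpha for suppression. Opposite-cue trials at the same coil position, in the same session and with the same trains, bear directly on it, but no specified analysis uses them.

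**Working it through.** **1. The plan's own figure.** Section 11.2 gives an effect size of 0.532 for the site-by-frequency interaction on capacity, 95% power and 48 participants. Alpha is not stated; two-sided 0.05 is assumed. A 2 × 2 within-participant interaction has one degree of freedom, so it equals a one-sample t-test on the contrast. With noncentrality 0.532 × √48 = 3.69 and 47 degrees of freedom, power is 95.0%, and 48 is the smallest such n. The same method returns the other two figures in section 11.2 (0.83 gives 21; 0.56 gives 44).

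**2. Arrhythmic subtraction.** Write K(site, cue, train) for the outcome, with sites F and P, cues R and L, and trains θ, α and arr.

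C = ½{[K(F,R,θ) − K(F,R,α)] + [K(P,L,α) − K(P,L,θ)]}

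With one arrhythmic cell per site and cue, (θ − arr) − (α − arr) = θ − α. The arrhythmic term drops out of C and out of the interaction.

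**3. What else cancels.** Let u be a non-specific θ − α difference at the frontal site and v the one at the parietal site, neither depending on cue. C shifts by (u − v)/2. If u = v the shift is zero. If u ≠ v it remains.

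**4. Size if it were present.** Let b = (u − v)/2 in SDs of C, with no true rhythm effect, n = 48 and two-sided 0.05. The documents give no value for b; this is a range.

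| b | Chance that C is significant |
|---|---|
| 0.1 | 10% |
| 0.2 | 27% |
| 0.3 | 53% |
| 0.4 | 78% |
| 0.532 | 95% |

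**5. Opposite-cue trials.** Define

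C0 = ½{[K(F,L,θ) − K(F,L,α)] + [K(P,R,α) − K(P,R,θ)]}

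A cue-independent nuisance effect shifts C0 by the same (u − v)/2, so it leaves C − C0. In simulation with no rhythm effect, the test of C − C0 rejected in 5.0% to 5.6% of runs across the nuisance sizes tried.

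**6. Power of C − C0 at n = 48.** Assume equal SDs and a within-participant correlation ρ between C and C0 (not given). Then dz = mean(C − C0)/√(2(1 − ρ)).

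- Wholly cue-specific effect: C = 0.532, C0 = 0, mean difference 0.532.
- Frontal half cue-independent, halves equal (assumed): C = (d + d)/2 = d and C0 = (d + 0)/2 = d/2, mean difference 0.266.

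| ρ | C0 = 0: dz, power | C0 = d/2: dz, power |
|---|---|---|
| 0 | 0.376, 72% | 0.188, 25% |
| 0.25 | 0.434, 84% | 0.217, 31% |
| 0.5 | 0.532, 95% | 0.266, 44% |

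Requiring both C and C − C0 to be significant gives, in simulation, 72%, 82% and 91% when C0 = 0, and 25%, 32% and 43% when C0 = d/2. C alone has 95%. For C − C0 to reach 95% power when C0 = 0 would take 94, 71 or 48 participants at ρ = 0, 0.25 or 0.5.

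**7. Trials per cell.** With an equal split over three trains and three cue types (an assumption), 600 trials per session (section 6.2) give 600/9 ≈ 67 per cell. The 200 to 300 trials implied by section 6.5.1 give 22 to 33.

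**The case against.** The sponsor can fairly answer on four grounds.

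- *The design is controlled.* It has an active control, and the crossed contrast removes any frequency-related distraction shared by the two sites. This stands. A reader might infer that the study lacks a negative control altogether; the documents do not support that. The gap is confined to a site-dependent difference between 5 Hz and 10 Hz trains.
- *The cancellation depends on how arrhythmic trains are built.* Section 11.1 promises matching by condition and duration. Theta and alpha trains last 800 and 400 ms, so that could mean two arrhythmic comparators. The subtraction would then not cancel in the ANOVA and would remove duration-related nuisance. This stands as an ambiguity. Against it, section 6.2 lists one arrhythmic train, and the effect defined in 2.3.1 and 2.3.3 has no arrhythmic term.
- *No distraction effect of this kind is shown.* Correct. Section 10.1 is an end-of-session list that separates neither frequency nor site. The percentages in step 4 are a power curve at assumed nuisance sizes, and 0.532 is simply the planned effect reused.
- *A cue-independent frontal benefit is itself hypothesised.* Section 11.1 accepts a frontal main effect of frequency, and section 2.1 links frontal theta to the number of items held. C0 need not be zero when the theory is right. It is tempting to make a significant C − C0 a condition of success, but that could fail a true effect: power could fall from 95% to 25–43%.

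None of this meets the remaining point. Section 11.1 hypothesises a frequency-by-cue interaction, and its model has no cue term.

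**Conclusion.** The point holds in a limited form. With one arrhythmic train type, the capacity and response-time compatibility effects reduce to theta minus alpha at one cue direction per site. They cannot distinguish cue-specific compatibility from a frequency effect that varies by site for another reason. The frequency-by-cue interaction hypothesised in section 11.1 cannot be tested by the planned ANOVA, although the trials that would inform it are collected.

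The documents do not show that such distraction exists, or that a significant result would be false. The size and sign of any bias are unknown. The value of C − C0 rests on distraction not depending on cue direction, and its power rests on ρ and on how cue-specific the true frontal effect is. The sample size calculation is sound for C and need not change. This is a worthwhile, inexpensive improvement to interpretation; it does not invalidate the primary analysis.

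**What to change.** Keep C as the primary effect and 48 completers. In sections 2.3 and 11.1:

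1. Prespecify, for capacity and response time, a supporting specificity analysis on the opposite-cue trials. Report C0 and C − C0 with confidence intervals, and frequency-by-cue separately within each site, so that a cue-independent frontal theta benefit can be seen as such.
2. State that cue-specific compatibility will be claimed only if C − C0 supports it in the hypothesised direction (negative for response time). State also that a significant C with a similar C0 does not by itself separate a cue-independent frequency effect from site-dependent distraction. Do not make C − C0 a gate for the primary result.
3. Reconcile the condition- and duration-matching wording in section 11.1 with the single arrhythmic train in section 6.2. Limit the claim that arrhythmic TMS controls non-specific effects to contrasts where it does not cancel.
4. Reconcile the trial counts in sections 6.2 and 6.5.1, since they set the precision of the opposite-cue cells.

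The cost is some added text and one supporting analysis per behavioural outcome, on data already recorded. The analysis may be inconclusive: its power is 72% to 95% if the effect is wholly cue-specific and 25% to 44% if the frontal half is not, for correlations of 0 to 0.5.

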2.3.2 PRIMARY OUTCOME – SPECTRAL POWER

RATIONALE. The electrical activity of the brain is recorded during performance of the task and during brain stimulation. The investigators will perform Morelet wavelet convolution on the recorded electrical signal to calculate the spectral power of theta (5-8 hertz) and alpha (8-12 hertz). Theta oscillations are known to be generated in frontal cortex when cued to the contralateral visual field. Alpha oscillations are known to be generated in parietal cortex when cued to the ipsilateral visual field.

ALTERNATIVE HYPOTHESIS. When the frequency of TMS to either frontal or parietal cortex is compatible with the endogenous activity, spectral power in the stimulated frequency band should increase relative to TMS that is incompatible. Therefore, we will report the TMS compatibility effect as the average of "theta power for theta minus alpha TMS to frontal cortex for retro-cue right" and "alpha power for alpha minus

theta TMS to parietal cortex for retro-cue left". We will report the mean and standard deviation of the TMS compatibility effect across participants. This effect will be investigated using repeated-measures two-way ANOVA, and an interaction between TMS site and TMS frequency is hypothesized.

NULL HYPOTHESIS. There is no systematic effect of frequency specific TMS on spectral power.

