6.2 SPECIAL ASSAYS OR PROCEDURES

Each participant will receive stimulation on all four sessions, separated by a week. The baseline session will involve single pulse TMS for calculating the motor threshold. The other three sessions will involve train of rhythmic TMS during performance of a cognitive control task. For stimulation day, the rhythmic TMS trains are delivered on every trial of the task (there are 600 trials per session). Each train of TMS consists of 5 pulses. There will be a total of 2400 pulses delivered per session. Each TMS train will be separated by a minimum of 5 seconds. There are three possible trains: alpha frequency with a 100 milliseconds inter-pulse interval, theta frequency with a 200 milliseconds inter-pulse interval, and arrhythmic with a variable inter-pulse interval (not to exceed a minimum of 20 milliseconds inter-pulse interval). The inter-pulse interval, inter-train interval, number of trains, and TMS intensity are all under the safety guidelines set forth by Rossi et al. 2009 and is typical for experiments that deliver online TMS (Hanslmayr et al. 2014; Albouy et al. 2017).

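### The spectral-power compatibility effect changes outcome band, site and cue together, so it is positive under own-band entrainment alone and cannot isolate compatibility

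*Combined protocol and SAP*

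**What the plan says.** Section 2.3.2 (spectral power, a primary outcome) predicts that "spectral power in the stimulated frequency band should increase relative to TMS that is incompatible". It then defines one summary per participant, the average of two terms:

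- frontal term: "theta power for theta minus alpha TMS to frontal cortex for retro-cue right";
- parietal term: alpha power for alpha minus "theta TMS to parietal cortex for retro-cue left".

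On testing, it adds: "This effect will be investigated using repeated-measures two-way ANOVA, and an interaction between TMS site and TMS frequency is hypothesized". The null hypothesis is: "There is no systematic effect of frequency specific TMS on spectral power".

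The aim behind this is in section 2.1: "To provide causal evidence that parietal cortex generates alpha activity and frontal cortex generates theta activity". The same section describes a full crossing: "By applying alpha frequency, theta frequency, and arrhythmic TMS at each location".

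Section 11.1 makes a two-way repeated-measures ANOVA the key analysis, with TMS frequency and site as factors, run on differences from arrhythmic TMS. It ties the cue to the site (right for frontal, left for parietal). Its spectral-power hypotheses are that theta TMS raises theta and alpha TMS raises alpha, each against arrhythmic TMS; neither names a site. No section states which band is the ANOVA outcome or which sensors supply the power. Section 6.2, on the trains, says: "There are three possible trains", namely alpha, theta and one arrhythmic.

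**The concern.** Compatibility is a claim about site: theta stimulation should do more where theta is the local rhythm, and alpha stimulation more where alpha is. Testing it means comparing the same band across sites. The reported summary never does so. Theta power enters only from the frontal site and alpha power only from the parietal site. Within each term only TMS frequency varies; between the terms band, site and cue all change at once.

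If rhythmic TMS simply raises power at its own frequency wherever the coil is placed, both terms are positive. A significant positive result on a primary outcome could then be read as support for the section 2.1 aim when it shows only that theta and alpha trains affect the spectrum differently.

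The band problem is confined to spectral power. The working-memory and response-time summaries use one measure at both sites. The tie between cue and site is common to all three outcomes.

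**Working it through.** **Plan's own figures.** Section 11.2 gives effect sizes 0.532, 0.83 and 0.56, with 48, 21 and 44 participants for 95% power. A paired t-test with two-sided 5% alpha (assumed; not stated) reproduces all three: power 95.05% at 48, 95.1% at 21 and 95.3% at 44. The sample-size arithmetic is not in question.

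**Model.** Write e_θ and e_α for the rise in a band when TMS is at that band's frequency, the same at both sites. Write g for the extra rise when the site is the compatible one. The other frequency is taken to leave the band at its arrhythmic level.

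- Reported effect = ½[(e_θ + g) + (e_α + g)] = (e_θ + e_α)/2 + g.
- Reversed pairing (theta power at parietal, alpha power at frontal) = (e_θ + e_α)/2.
- Within-band contrast = ½[(theta power: theta−alpha TMS, frontal minus parietal) + (alpha power: alpha−theta TMS, parietal minus frontal)] = g. This is the reported effect minus the reversed one.
- ANOVA interaction, band fixed by site = e_θ + e_α + 2g, twice the reported effect.
- ANOVA interaction, stimulated band minus same-band arrhythmic = (e_θ + g − e_α) − (e_θ − e_α − g) = 2g.

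**Arrhythmic control.** Within one term, site, cue and band are constant. With one arrhythmic value A, (theta − A) − (alpha − A) = theta − alpha, so A cancels. If each frequency had its own arrhythmic train, A would not cancel exactly, but e is itself a gain over arrhythmic TMS and would remain.

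**With the plan's effect sizes.** Setting e_θ = 0.56, e_α = 0.83 and g = 0 gives (0.56 + 0.83)/2 = 0.695, not 0. This assumes that the sizes carry over from rhythmic-versus-arrhythmic to theta-versus-alpha comparisons, with unit SD per term. Power at 48 to declare the effect non-zero is then at least 99.8% for a correlation of 0 to 0.9 between the terms.

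**With smaller entrainment.** Assume n = 48, independent cells with SD 1, e_θ = e_α = d, g = 0, and power read at the same position relative to the coil.

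- Variance of the reported contrast (4 cells, weights ±½) = 4 × ¼ = 1; SD 1.00.
- Variance of the within-band contrast (8 cells, weights ±½) = 8 × ¼ = 2; SD 1.41.
- Noncentrality of the reported contrast = d√48 = 1.39, 2.08 and 3.46 on 47 df.

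| Test, two-sided 5% | d = 0.2 | 0.3 | 0.5 |
|---|---|---|---|
| Reported contrast | 27% | 53% | 92% |
| Reversed pairing | 27% | 53% | 92% |
| ANOVA, band fixed by site | 27% | 53% | 92% |
| Within-band contrast | 5% | 5% | 5% |
| ANOVA, stimulated band minus arrhythmic | 5% | 5% | 5% |

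Simulation (10,000 trials per setting) agrees. The reported contrast gave 0.278, 0.531 and 0.921, the reversed pairing 0.285, 0.533 and 0.929, and the within-band contrast 0.048, 0.050 and 0.051.

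**Sensors.** Suppose theta is always read at frontal sensors and alpha at parietal sensors, and entrainment stays local to the coil. Theta TMS at the parietal site then leaves frontal theta unchanged, so the within-band contrast has mean d with SD 1.41. It rejects in 16%, 30% and 67% with no rhythm specificity, and the stimulated-band ANOVA does much the same (17%, 29% and 68% in simulation). With half the entrainment spreading to the other site, the within-band rates are about 8%, 11% and 22%. Under local entrainment the reversed pairing falls to about 5%, so its equality with the reported contrast holds only for same-position sensors.

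**The case against.** **The plan already treats this outcome as entrainment.** Section 11.1 words its hypotheses that way, section 11.2 sizes the EEG comparisons on rhythmic versus arrhythmic power, and the 2.3.2 null is any frequency-specific effect on power. This stands: the reported contrast is a valid test of that null. What remains unsupported is the compatibility label and the use of the result for the section 2.1 aim.

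**The contrast still contains compatibility.** A reader might infer that it measures entrainment and nothing else. The algebra does not support that: with e = 0 and g = 1 it equals 1. It mixes the two and cannot separate them.

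**The inferential test may be sound.** The summary is reported as a mean and SD; the test is the ANOVA. Section 2.3.2 says that this same effect goes into the ANOVA, which points to a band fixed by site. Its reference to the stimulated band, together with the section 11.1 hypotheses, points to stimulated-band minus same-band arrhythmic power, which lacks the fault under same-position sensors. Both readings are open, so calling the primary test wrong would go too far.

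**The arrhythmic control is condition-matched.** Section 11.1 says so, but matching removes non-specific effects of pulses, not the frequency-specific gain e.

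**The rejection rates rest on supplied assumptions.** Equal entrainment, unit SD and independent cells are not in the documents. The rates are illustrations; the algebra does not depend on them.

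**Conclusion.** The point holds in a limited form. The 2.3.2 spectral-power effect equals mean own-band entrainment plus any site-specific gain, so a positive value cannot be read as compatibility. Under the stated assumptions, entrainment of 0.2 to 0.5 SD with no site specificity makes it significant in 27% to 92% of trials, with the same rates for the opposite pairing. Equal entrainment at both sites is an assumption, but nothing in the plan rules it out. The ANOVA shares the fault only if its band is fixed by site, and the plan does not say.

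A reader might also infer that 48 participants are too few for the corrected test. The documents do not support that. The section 11.2 EEG effect sizes concern rhythmic versus arrhythmic TMS, so they describe e and say nothing about g. Under the independent-cell model that two-cell difference also has SD 1.41, so an effect with the same raw size as 0.56 would keep 96.7% power at 48.

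This should be settled before the EEG is analysed. It does not affect the band-free working-memory and response-time contrasts.

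**What to change.** 1. Keep the 2.3.2 contrast, but label it an entrainment check.
2. Test compatibility with the average of two within-band site-by-frequency interactions. For theta power, take theta minus alpha TMS, frontal minus parietal; for alpha power, take alpha minus theta TMS, parietal minus frontal. Alternatively, state that the ANOVA outcome is stimulated-band minus same-band arrhythmic power. Say which is primary.
3. Specify that power is read at the same position relative to the stimulated site for both sites. Fixed frontal-theta and parietal-alpha sensors bring the fault back when entrainment is local.
4. State that cue direction remains aliased with site, or compare the sites at matched cue direction as a sensitivity analysis; the task in section 6.5.1 includes left and right cues.
5. In section 11.2, tie the EEG effect sizes 0.83 and 0.56 to the entrainment check only.

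**Cost.** Analysis-plan wording and one added contrast on EEG already planned in every site-by-frequency cell. Under independent cells the within-band contrast has an SD about 1.41 times that of the reported one. With 48 participants it has about 80% power for d = 0.41 and 95% for d = 0.53, in units of its own SD (0.41 × 1.41 = 0.58 and 0.53 × 1.41 = 0.75 cell SDs).
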